5.0 Analysis Populations

5.1 Definitions for Analysis Populations

5.1.1 Intention-to-Treat (ITT) Population

All enrolled subjects who receive at least one dose of study drug will be included in the ITT population. Demographic, baseline characteristics, exposure, compliance, concomitant medication and medical history analyses will be performed on the ITT population overall and according to the treatment arm assignment, i.e., subject grouping will be based on the arm to which the subject was assigned. Demographic and baseline characteristics will also be summarized by GT. Efficacy analyses will be performed by GT (GT5 and GT6) and for the overall ITT population.

5.1.2 Modified Intention-to-Treat (mITT) Populations

Sensitivity analyses of SVR₁₂ as described in Section 10.5, when applicable, will be performed on the ITT population modified to exclude subjects who do not have HCV GT5 or 6 infection or with multiple/mixed genotypes (final HCV genotype as determined in Section 10.8) (mITT-GT), and on the mITT-GT population further modified to exclude subjects who do not achieve SVR₁₂ for reasons other than virologic failure (mITT-GT-VF).

5.1.3 Safety Population

All subjects who receive at least one dose of study drug will be included in the safety population. Safety analyses will be performed on the overall safety population, combining Arms A and B.

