4.0 Study Objective

4.1 Primary Objectives

The primary objectives of this study are to assess the efficacy (by evaluating the percentage of subjects achieving SVR₁₂) and safety of glecaprevir/pibrentasvir in adults with chronic hepatitis C virus (HCV) genotype (GT) 5 or 6 infection with or without compensated cirrhosis. The efficacy of glecaprevir/pibrentasvir will be assessed by genotypes across treatment durations (or cirrhosis status) and the safety of glecaprevir/pibrentasvir will be assessed by treatment duration (or cirrhosis status) across genotypes.

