8.1.5 Safety

Safety summaries will be provided by the treatment arm (i.e., cirrhosis status/study drug duration) and overall. All subjects who receive at least one dose of study drug will be included in the safety analyses.

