4.0 Study Objectives, Design and Procedures

4.1 Objectives

The primary objectives of this study are to assess the efficacy (by evaluating the percentage of subjects achieving a 12-week sustained virologic response, SVR₁₂) and safety of GLE/PIB in adults with chronic HCV GT5 or 6 infection with or without compensated cirrhosis.

The secondary objectives are to assess the efficacy of GLE/PIB in adults with HCV GT 5 or 6 infection with or without compensated cirrhosis by evaluating the percentages of subjects with on-treatment virologic failure and post-treatment relapse.

[figure not shown]

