11.0 Safety Analysis

11.1 General Considerations

Safety data will be summarized using the safety population. Data will be summarized for the overall population across genotype and across treatment arm.

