11.3.2 Statistical Methods

The baseline value for clinical laboratory tests will be the last non-missing measurement on or before the day of the first dose of study drug. Values on Day 1 must also be before the time of first dose if time is available. The same baseline value will be used for changes to Treatment Period visits and changes to Post-Treatment Period visits.

Visit Values

For each laboratory parameter listed in Section 11.3.1, values at each visit (baseline and post-baseline, including applicable post-treatment visits) will be summarized with the

sample size, mean, standard deviation, minimum, median, and maximum. Figures presenting mean values over time will be produced.

Change from Baseline

For each laboratory parameter listed in Section 11.3.1, changes from baseline to each post-baseline visit, including applicable post-treatment visits, will be summarized with the sample size, baseline mean; visit mean; and change from baseline mean, standard deviation, minimum, median, and maximum.

Shift Tables

Individual changes in the laboratory parameters listed in Section 11.3.1 will be tabulated using shift tables. Laboratory data values will be categorized as low, normal, or high based on normal ranges of the laboratory used for each sample. Shift tables from baseline to minimum value and maximum value during the Treatment Period will be created. For each parameter, the shift tables will cross tabulate the frequency of subjects with baseline values below/within the normal range to maximum above the normal range and with baseline values within/above the normal range to minimum below the normal range.

Maximum Toxicity Grade

The laboratory parameters listed in Table 9 will be assigned a toxicity grade of 1, 2, 3, or 4. The number and percentage of subjects with a maximum toxicity grade of 1, 2, 3 or 4 during the Treatment Period will be tabulated. To be counted, the post-baseline value must have a toxicity grade that is more extreme than the toxicity grade corresponding to the baseline value. For each laboratory parameter in Table 9, the summary will also include the number and percentage of subjects with a maximum of at least Grade 3. A listing of all relevant laboratory parameters will be provided for each subject who had an increase to Grade 2 or higher for any laboratory variable in Table 9.

Assessment of Hepatic Laboratory Values

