12.0 Summary of Changes

12.1 Summary of Changes Between the Latest Version of the Protocol and SAP Version 1.0

1. New expected confidence intervals are calculated in Section 4.3 Sample Size because the rule of choosing between the normal approximation method and

Wilson's score method for the primary endpoint has been updated in the protocol (also see Section 10.3)

2. All safety analyses have been changed to be performed only for the overall population because integrated safety analyses on Phase 3 studies showed no difference in safety profiles between subjects with compensated cirrhosis and without cirrhosis.
3. The race category of Black/non-Black has been changed to Asian/non-Asian in Section 7.1 and Section 10.6 because the Asian population is of interest to this study while very few Black subjects are expected to enroll. Also, different Asian types will be summarized among the baseline characteristics (Section 7.1).
4. The category of baseline HCV RNA level has been changed from 6,000,000 IU/mL to 2,000,000 IU/mL because it is a better cutoff based on previous studies.
5. Efficacy endpoints will also be summarized for the overall population (Section 10.6, Section 10.7 and Section 10.9) in order to provide results across all subjects in the study.
6. The integrated efficacy analysis combining GT5 and GT6 subjects from Studies M14-868 Part 4, M14-172 and M16-126 using meta-analytic methods has been removed because there is no plan for a label update with such data.
7. The resistance analyses (Section 10.8) have been updated to reflect current HCV project standards.
8. Text in PRO analyses of mean change from baseline has been updated for better clarity (Section 10.9).
9. Missing data handling conventions for scores related to the Work Productivity and Activity Impairment Questionnaire (WPAI) – Hepatitis C are specified in Section 10.9.
10. Methods for the assessment of hepatic laboratory values and hepatic laboratory abnormalities of interest have been added to Section 11.3.2 to reflect current HCV project standards.

11. The summaries of changes from baseline for vital signs have been replaced with summaries of visit values to reflect current HCV project standards (Section 11.4.2).

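### The SAP tabulates adverse events, laboratory data and vital signs only for Arms A and B combined, although the protocol still requires them by arm and overall

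*SAP*

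**What the plan says.** **Protocol.** After naming efficacy and safety as primary objectives, section 4.1 adds that "the safety of glecaprevir/pibrentasvir will be assessed by treatment duration (or cirrhosis status) across genotypes". Section 8.1.5 carries this into the analysis: "Safety summaries will be provided by the treatment arm (i.e., cirrhosis status/study drug duration) and overall". Section 8.1.5.3 asks for mean change from baseline in vital signs at each post-baseline visit.

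**SAP.** Section 4.1 restates the objective as "safety of GLE/PIB in adults with chronic HCV GT5 or 6 infection with or without compensated cirrhosis" and omits the sentence on duration or cirrhosis status. Section 5.1.3 says "Safety analyses will be performed on the overall safety population, combining Arms A and B", and section 11.1 says "Data will be summarized for the overall population across genotype and across treatment arm". Section 12.1, item 2, declares the departure: "All safety analyses have been changed to be performed only for the overall population". The reason given is that integrated Phase 3 safety analyses showed no difference between subjects with and without compensated cirrhosis. Item 11 separately replaces vital-sign change from baseline with visit values.

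**Visits and figures.** SAP 4.2 and Table 1 give the on-treatment Week 12 visit to Arm B only. For laboratory parameters, SAP 11.3.2 summarises values at every visit and adds: "Figures presenting mean values over time will be produced".

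**The concern.** The protocol asks a question about safety by duration or cirrhosis status, and the SAP plans no summary table that answers it. The reason given comes from outside this trial, so it settles the question before the trial's own data are tabulated. Protocol 5.6.1 itself calls the GT5 and GT6 numbers in the Phase 3 cirrhosis study small (3 and 7), so up to about 16 further cirrhotic subjects are a meaningful addition.

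Two things are at stake. Event rates in the smaller, cirrhotic arm are read against a denominator made up mostly of non-cirrhotic 8-week subjects. Pooled visit means also change composition abruptly at Week 12, which can look like a drug effect over time.

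**Working it through.** The plan states no precision or sample-size figure for safety, so there is none to reproduce. The check is a comparison of texts followed by simple arithmetic.

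**1. What is still produced by arm in the SAP**

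| Output | By arm? | SAP section |
|---|---|---|
| Listing of treatment-emergent adverse events | Yes | 11.2.2 |
| Discontinuation reasons, drug interruptions | Yes | 8.1 |
| Exposure, compliance | Yes | 9.0 to 9.2 |
| Adverse event summary tables | No | 5.1.3, 11.1 |
| Laboratory summaries and mean plots | No | 5.1.3, 11.1, 11.3.2 |
| Vital-sign summaries | No | 5.1.3, 11.1, 11.4.2 |

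Adverse event counts by arm could be rebuilt by hand from the listing. By-arm laboratory and vital-sign summaries could not be obtained from the planned output.

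**2. Effect on event rates**

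Inputs from Protocol 8.2: about 80 subjects, of whom up to about 16 have cirrhosis. At the cap, Arm B = 16, Arm A = 64 and the Arm B share is 16/80 = 20%.

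The Wilson 95% limits, with p = x/n and z = 1.96, are [p + z²/2n ± z√(p(1−p)/n + z²/4n²)] / (1 + z²/n). With x = 0 the upper limit reduces to z²/(n + z²).

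- One event, in Arm B: 1/16 = 6.3% (1.1 to 28.3%). Pooled: 1/80 = 1.3% (0.2 to 6.7%).
- No events, Arm B: upper limit 3.84/(16 + 3.84) = 19.4%. Pooled: 3.84/(80 + 3.84) = 4.6%.
- No events, if Arm B enrols only 8 (an assumption; the documents set no minimum): 3.84/(8 + 3.84) = 32.4%.

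**3. Effect on visit means at Week 12**

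Let a be the Arm A mean and a + D the Arm B mean, both constant over time, with full attendance.

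- Through Week 8 the pooled mean is 0.8a + 0.2(a + D) = a + 0.2D.
- At Week 12 only Arm B contributes, so the mean is a + D.
- Apparent step: (a + D) − (a + 0.2D) = 0.8D, with no within-subject change. With Arm B at 8 of 80 it is 0.9D.

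The size of D is not in the documents. A non-zero D is plausible for some parameters: Protocol 5.2.2 sets different platelet and albumin limits by cirrhosis status, and the FibroTest route in Protocol 5.3.1.1 requires APRI below 1 for non-cirrhotic and above 2 for cirrhotic subjects.

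**4. Which planned output would reveal the step**

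- Laboratory: SAP 11.3.2 keeps change from baseline at each visit with sample size, baseline mean and visit mean. If the baseline mean is taken over subjects with a value at that visit, the Week 12 row shows the smaller n and no mean change. The table would expose the step; the plot would not.
- Vital signs: SAP 11.4.2 gives visit values only, with no mean-change summary.

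**The case against.** The strongest reply is that this is a declared, reasoned change. The cited Phase 3 analyses are not in the documents, so their adequacy cannot be judged here. No hypothesis is tested, Arm B is small, and duration is fully confounded with cirrhosis. Power to separate the arms would be low: with 64 and 16 subjects, about 39% for assumed rates of 2% against 10%, and 51% for 5% against 20%. All this stands, and it limits by-arm tables to description. Description is what Protocol 8.1.5 asks for, and the SAP already accepts by-arm columns for disposition, exposure and compliance.

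The reply also rightly blocks several stronger readings that a reader might infer:

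- *That all safety output is pooled.* It is not; see the table in the working.
- *That the trial cannot report a primary objective at all.* The overall safety objective is served by the pooled tables. What is lost is the part on duration or cirrhosis status.
- *That a hepatic event in Arm B would be hidden.* Hepatic decompensation and hepatocellular carcinoma events have by-subject listings (SAP 11.2.3), as do subjects meeting hepatic laboratory criteria (SAP 11.3.2). The dilution affects the tabulated percentage.
- *That the Week 12 step would mislead throughout the laboratory output.* The retained change table would reveal it.
- *That vital signs are plotted, or keep no within-subject measure.* No vital-sign figure is specified, and every criterion in SAP Table 10 uses change from the subject's own baseline.

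Amending the protocol objective would also remove the contradiction. It would leave the Week 12 step in place and give up information that the trial collects anyway.

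**Conclusion.** The point holds in limited form. The SAP contradicts an unamended part of the protocol's primary objectives and leaves it without a tabulated analysis. Declaring the change in SAP 12.1 makes it transparent but does not answer the question that the protocol still asks.

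At the cap of 16 in 80, pooling divides the tabulated rate of an event seen only in Arm B by 80/16 = 5 and cuts the zero-event upper limit from 19.4% to 4.6%. The five-fold figure assumes that Arm B fills to its cap and that Arm A has no such event. The 0.8 × D step assumes the same split, constant arm means and full attendance. It concerns the on-treatment Week 12 visit only: Final Treatment and Post-Treatment Week 12 values include both arms.

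Efficacy, sample size and error rates are untouched. This is a should-fix and a cheap improvement, not a flaw that stops the trial from reporting safety.

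**What to change.** - In SAP 5.1.3 and 11.1, restore descriptive adverse event, laboratory and vital-sign summaries for Arm A, Arm B and overall, and revise item 2 of SAP 12.1 to match.
- In SAP 11.3.2, draw the laboratory mean plots by arm, or label Week 12 as Arm B only.
- In SAP 11.4.2, restore mean change from baseline for vital signs, as in Protocol 8.1.5.3, and revise item 11 of SAP 12.1. That item is a separately declared change. It belongs here because vital signs otherwise have no mean-change table to expose the Week 12 step.

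The cost is SAP wording, two extra table columns, a plot specification and the vital-sign change table, with no new data. The drawback is that Arm B percentages rest on at most about 16 subjects; they should be presented as descriptive, without comparison between arms.

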6.0 Analysis Conventions

6.1 Definition of Baseline, Final Treatment, and Final Post-Treatment Assessments

6.1.1 Baseline

The baseline value refers to the last non-missing measurement collected before the first dose of study drug is received.

The protocol specifies that all Day 1 assessments are to be performed prior to administering the first dose of study drug. Therefore, all Day 1 assessments for which time is not collected will be assumed to be pre-dose and the baseline value will be the last non-missing measurement collected on or before the first day of study drug administration. All Day 1 assessments with time collected must be before the time of first dose to be considered baseline and the last non-missing measurement collected before the date and time of the first dose of study drug will be considered the baseline value. If multiple measurements that are prior to dosing are recorded on the same date and with the same time or if time is not available, then the average of these measurements will be considered the baseline value.

The same baseline value will be used for analyses of both the Treatment and Post-Treatment Periods.

Safety assessments that are related to a serious adverse event that occurred on the first dose day are excluded when applying this algorithm.

6.1.2 Study Days

Study Days (Days Relative to the First Dose of Study Drug)

Study days are calculated for each time point relative to the first dose of study drug. Study days are negative values when the time point of interest is prior to the first study drug dose day. Study days are positive values when the time point of interest is after the

first study drug dose day. There is no Study Day 0. Study Day 1 is the day of the first dose of study drug.

Study Drug End Days (Days Relative to the Last Dose of Study Drug)

Study drug end days are calculated for each time point relative to the last dose of study drug. The last day of study drug dosing is defined as Study Drug End Day 0. Days before it have negative study drug end days and days after it have positive study drug end days.

Final Treatment Value

The final treatment value is defined as the last non-missing measurement collected after Study Day 1 and on or before Study Drug End Day 2.

Final Post-Treatment Value

The final post-treatment value for each subject is the last non-missing measurement collected after Study Drug End Day 2 and on or before Study Drug End Day 999.

6.2 Definition of Analysis Windows

For efficacy analyses of HCV RNA and resistance, the time windows specified in [Table 1](#) and [Table 2](#) describe how these data are assigned to protocol-specified time points during the Treatment and Post-Treatment Periods, respectively. All time points and corresponding time windows are defined based on the date/time of blood sample collection.

For safety laboratory data, patient reported outcome (PRO) data and vital sign data, the time windows specified in [Table 1](#) and [Table 3](#) describe how data are assigned to protocol-specified time points.

If more than one assessment is included in a time window, the assessment closest (except for when used in analyses of SVR) to the nominal time will be used. If there are

two observations equally distant to the nominal time, the latest one will be used in analyses. For analyses of SVR (e.g., SVR₁₂), the last value in the window will be used.

If multiple measurements are made on the same day for a safety laboratory parameter or a vital sign parameter, the average of the values will be used to calculate descriptive statistics and in analyses of the mean change from baseline. For summaries of shifts from baseline and potentially clinically significant values, multiple values on the same day will not be averaged; all values will be considered for these analyses.

Table 1. Analysis Time Windows for HCV RNA, Resistance Endpoints, Safety Laboratory, Vital Sign Measurements, and PRO Instruments (Treatment Period)

Scheduled Visit	Nominal Day (Study Day)	Time Window (Study Day Range)
Day 1/Baseline ^a	1	≤ 1 ^a
Week 1	7	2 to 10
Week 2	14	11 to 21
Week 4	28	22 to 42
Week 8	56	43 to 70
Week 12 ^b	84	71 to 98
Final Treatment Visit ^c	2 to ≤ 2 days after last dose of study drug	

a. Day of first dose of study drug.

b. For Arm B only.

c. The last value within the window will be used to define the Final Treatment Visit value. The upper bound of this Final window is Study Drug End Day 2. Study Drug End Day 0 is defined as the day of the last dose of study drug.

Note: For all windows, data must be on or before Study Drug End Day 2. The result closest to the scheduled time point will be used. PRO instruments are collected at Day 1 Visit and End of Treatment Visit (Week 8 for Arm A and Week 12 for Arm B, or Premature Discontinuation Visit).

Table 2. Analysis Time Windows for HCV RNA and Resistance Endpoints (Post-Treatment Period)

Scheduled Visit ^a	Nominal Day (Study Drug End Day)	Time Window (Study Drug End Day Range)
Post-Treatment Week 4	28	3 to 56
Post-Treatment Week 12	84	57 to 126
Post-Treatment Week 24	168	127 to 999
SVR ₄ ^b	28	3 to 56
SVR ₁₂ ^b	84	57 to 126
SVR ₂₄ ^b	168	127 to 210

a. Post-Treatment Visits are applicable to subjects who received at least one dose of study drug.

b. For SVR windows, the last value in the window will be used.

Note: The result closest to the scheduled time point will be used, except for SVR₄, SVR₁₂, and SVR₂₄. For all windows, data must occur after Study Drug End Day 2. Study Drug End Day 0 is defined as the day of the last dose of study drug.

Table 3. Analysis Time Windows for Safety Laboratory, Vital Sign Measurements, and PRO Instruments (Post-Treatment Period)

Scheduled Time ^a	Nominal Day (Study Drug End Day)	Time Window (Study Drug End Days Range)
Post-Treatment Week 4	28	3 to 56
Post-Treatment Week 12	84	57 to 126
Post-Treatment Week 24	168	127 to 999
Final Post-Treatment Visit ^b	> 2 days after last dose of study drug	

a. Post-Treatment Visits are applicable for subjects who received at least one dose of study drug.

b. The last value within the Post-Treatment Period window will be used to define the Final Post-Treatment value. The lower bound of this Final window is Study Drug End Day 3. Study Drug End Day 0 is defined as the day of the last dose of study drug.

Note: The result closest to the scheduled time point will be used. For all windows, data must occur after Study Drug End Day 2. Vital signs are collected at every Post-Treatment visit; hematology, chemistry, urinalysis, and coagulation panels are collected at Post-Treatment Week 4 Visit or at Post-Treatment Discontinuation Visit if subject discontinues prior to Post-Treatment Week 4. PRO instruments are collected at Post-Treatment Week 12 Visit.

6.3 Missing Data Imputation

Missing Data Imputation for SVR

HCV RNA values will be selected for analysis based on the analysis windows defined in Section 6.2.

For analyses of SVR, subjects' missing visit values will have backward imputation applied, if possible. For backward imputation, if the nearest HCV RNA value after the SVR window is unquantifiable or undetectable, then it will be used to impute the HCV RNA value in the SVR window. If a subject is missing an HCV RNA value within the appropriate SVR window after performing backward imputation, then this value will be imputed with an HCV RNA value from a local laboratory if present; otherwise, the HCV RNA value will be missing. Subjects with missing HCV RNA data in the analysis window, after imputations, will be imputed as a failure.

Regardless of the imputation method described above, if a subject starts another treatment for HCV, then all HCV RNA values for this subject measured on or after the start date of the new HCV treatment will be excluded from analyses. The subject will be considered a failure for summaries of viral response at all time points after the start of the new HCV treatment.

Missing Data Imputation for Virologic Failure

If HCV RNA values from the central laboratory are missing but a local laboratory value is present in the appropriate time period, then the local laboratory value will be used to assess post-treatment relapse and on-treatment virologic failure.

Missing Data Imputation for PRO Questionnaires

The handling of missing data for PROs will be as follows. If a respondent answers at least 50% of the items in a multi-item scale of the Short Form 36 Version 2 (SF-36v2) Health Status Survey, the missing items will be imputed with the average score of the answered items in the same scale. In cases where the respondent did not answer at least

50% of the items, the score for that domain will be considered missing. The Mental and Physical Component Summary measures will not be computed if any domain is missing. Missing data handling conventions for scores related to the Work Productivity and Activity Impairment Questionnaire (WPAI) – Hepatitis C are specified in Section 10.9.

